RBV	Ribavirin
RNA	Ribonucleic acid
RT-PCR	Reverse transcriptase PCR
SAE	Serious adverse event
sAFP	Serum Alpha-Fetoprotein
SAS	Statistical Analysis System
SD	Standard Deviation
SDP	Study Designated Physician
SGOT	Serum glutamic oxaloacetic transaminase
SGPT	Serum glutamic pyruvic transaminase
SOC	System Organ Class
SOF	Sofosbuvir
SUSAR	Suspected Unexpected Serious Adverse Reaction
SVR	Sustained virologic response
SVR ₄	Sustained virologic response 4 weeks post dosing
SVR ₁₂	Sustained virologic response 12 weeks post dosing
SVR ₂₄	Sustained virologic response 24 weeks post dosing
TP	Treatment Period
ULN	Upper limit of normal
USP	United States Pharmacopoeia
VAFS	Visual analogue fatigue scale

VAS	Visual analogue scale
WBC	White blood cells

Pharmacokinetic and Statistical Abbreviations

AUC	Area under the plasma concentration-time curve
C_{\max}	Maximum observed plasma concentration
C_{trough}	Trough plasma concentration
T_{\max}	Time to maximum observed plasma concentration

Definition of Terms

Study Drug	Ombitasvir/ABT-450/r, sofosbuvir, ribavirin
Screening Period	Up to 35 days prior to Study Day 1
Study Day 1	First day of study drug dosing
Treatment Period	Baseline/Day 1 through last dose of study drug
Post-Treatment Period	Day after last dose of study drug through Post-Treatment Week 48 or Post-Treatment Discontinuation

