6.3 Relationship to Study Drug

The investigator will use the following definitions to assess the relationship of the adverse event to the use of study drug. Assessment of relatedness will be made with respect to the DAAs (ombitasvir/ABT-450/r and SOF) and with respect to RBV:

Reasonable Possibility	An adverse event where there is evidence to suggest a causal relationship between the study drug and the adverse event.
No Reasonable Possibility	An adverse event where there is no evidence to suggest a causal relationship between the study drug and the adverse event.

For causality assessments, events assessed as having a reasonable possibility of being related to the study drug will be considered "associated." Events assessed as having no reasonable possibility of being related to study drug will be considered "not associated." In addition, when the investigator has not reported a causality or deemed it not assessable, AbbVie will consider the event associated.

If an investigator's opinion of no reasonable possibility of being related to study drug is given, an "Other" cause of event must be provided by the investigator for the SAE.

[figure not shown]
6.4

Adverse Event Collection Period

All serious adverse events as well as protocol-related nonserious adverse events will be collected from the time the subject signed the study-specific informed consent until study drug administration. From the time of study drug administration until 30 days following discontinuation of study treatment has elapsed, all adverse events and serious adverse events will be collected, whether solicited or spontaneously reported by the subject. In addition, serious adverse events will be collected from the time the subject signed the study-specific informed consent until 30 days after the last dose of study drug.

Adverse event information will be collected as shown in [Figure 2](#).

Figure 2. Adverse Event Collection

6.5

Adverse Event Reporting

In the event of a SAE, whether associated with study drug or not, the Investigator will notify Clinical Pharmacovigilance within 24 hours of the site being made aware of the SAE by entering the SAE data into the electronic data capture (EDC) system. SAEs that occur prior to the site having access to the RAVE® system or if RAVE is not operable should be faxed to Clinical Pharmacovigilance within 24 hours of being made aware of the SAE.

Ombitasvir/ABT-450/Ritonavir
M14-567 Protocol
EudraCT 2014-003147-35

FAX to: [REDACTED]

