8.1.5.1 Adverse Events

Adverse events will be coded using the Medical Dictionary for Regulatory Activities (MedDRA).²⁴ The number and percentage of subjects with treatment-emergent adverse events (i.e., any event that begins or worsens in severity after initiation of study drug through 30 days post-study drug dosing) will be tabulated by primary MedDRA System Organ Class (SOC) and preferred term (PT) for each treatment arm and overall. The tabulation of the number of subjects with treatment-emergent adverse events by severity rating and relationship to study drug will also be provided. Subjects reporting more than one adverse event for a given MedDRA preferred term will be counted only once for that term using the most severe incident for the severity rating table and the most related for the relationship to study drug table. Subjects reporting more than one type of event within a SOC will be counted only once for that SOC.

Additional analyses will be performed if useful and appropriate.

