11.2.1.1 Tabulations of Treatment-Emergent Adverse Events

Adverse event data will be summarized and presented using primary MedDRA system organ classes (SOCs) and preferred terms (PTs) by treatment arm according to the version of the MedDRA coding dictionary used for the study at the time of database lock. The

actual version of the MedDRA coding dictionary used will be noted in the clinical study report. The system organ classes will be presented in alphabetical order and the preferred terms will be presented in alphabetical order within each system organ class.

Adverse Event Overview

An overview of adverse events will be presented consisting of the number and percentage of subjects experiencing at least one event for the following adverse event categories:

- Any treatment-emergent adverse event;
- Treatment-emergent adverse events with a "reasonable possibility" of being related to DAAs (Ombitasvir/ABT-450/r);
- Treatment-emergent adverse events with a "reasonable possibility" of being related to RBV (applicable for RBV-containing arms);
- Severe treatment-emergent adverse events;
- Serious treatment-emergent adverse events;
- Treatment-emergent adverse events leading to discontinuation of study drug;
- Treatment-emergent adverse events leading to interruption of study drug;
- Treatment-emergent adverse events leading to RBV dose modification (applicable for RBV-containing arms);
- Treatment-emergent adverse events leading to death;
- Deaths.

The adverse event overview summary will be provided for each treatment arm.

Adverse Event by SOC and PT

The following summaries of adverse events will be generated by treatment arm:

- Treatment-emergent adverse events;
- Treatment-emergent adverse events with a "reasonable possibility" of being related to DAAs (Ombitasvir/ABT-450/r);

- Treatment-emergent adverse events with a "reasonable possibility" of being related to RBV;
- Serious treatment-emergent adverse events;
- Moderate or severe treatment-emergent adverse events;
- Severe treatment-emergent adverse events;
- Grade 3 or 4 (see definition below) treatment-emergent adverse events;
- Treatment-emergent adverse events leading to discontinuation of study drug;
- Treatment-emergent adverse events leading to interruption of study drug;
Treatment-emergent adverse events leading to RBV dose modification;
- Treatment-emergent adverse events leading to death;
- Treatment-emergent adverse events leading to concomitant medication use

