(events with other action taken of "concomitant medication prescribed").

For all adverse event summaries, the number and percentage of subjects experiencing treatment-emergent adverse events will be tabulated according to SOC and PT. Subjects reporting more than one adverse event for a given PT will be counted only once for that term (most severe incident for the severity tables and most related incident for the relationship tables). Subjects reporting more than one adverse event within a SOC will be counted only once for that SOC. Subjects reporting more than one adverse event will be counted only once in the overall total.

A listing of treatment-emergent adverse events grouped by body system and preferred term with subject numbers will be created for each treatment arm.

Adverse Event by PT

The number and percentage of subject experiencing treatment-emergent adverse events will be tabulated according to preferred term and sorted by overall frequency for the total number of subjects in each treatment arm. Similar summaries will be provided for moderate to severe treatment-emergent adverse events and treatment-emergent adverse events with a "reasonable possibility" of being related to DAAs. These summaries will display for each treatment group and be sorted by overall total.

Adverse Event of Special Interest

Specific treatment-emergent adverse events of special interest, which may be searched using Standardized or Company MedDRA Queries, will be summarized and include severe cutaneous reactions and anemia. The search criteria for the adverse event of interest are as follows:

- Severe Cutaneous Reactions
SMQ "Severe cutaneous adverse reactions" (narrow search)
- Anemia
SMQ "Haematopoietic erythropenia" (broad search) plus the following preferred terms:
Haemolytic anaemia,
Coombs negative haemolytic anaemia,
Coombs positive haemolytic anaemia.

For each adverse event of interest (severe cutaneous reactions and anemia), the number and percentage of subjects experiencing at least one treatment-emergent adverse event in the search for the event of interest will be presented for each treatment arm and overall and by SOC and PT.

A listing of treatment-emergent adverse events for subjects meeting the search criterion will be provided for the adverse event of special interest.

Adverse Event by Maximum Severity

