Treatment-emergent adverse events and treatment-emergent adverse events with a "reasonable possibility" of being related to DAAs will be summarized by maximum severity of each preferred term. If a subject has an adverse event with unknown severity, then the subject will be counted in the severity category of "unknown," even if the subject has another occurrence of the same event with a severity present. The only exception is if the subject has another occurrence of the same adverse event with the most extreme severity – "Severe." In this case, the subject will be counted under the "Severe" category.

Adverse Events by Maximum Severity Grade Level

Treatment-emergent adverse events will be summarized by maximum severity grade level of each preferred term. Each preferred term will be assigned to a grade level based on severity and seriousness, adapted from the Division of AIDS (DAIDS) table for grading severity of adverse events. All serious adverse events will be categorized as Grade 4. Nonserious adverse events categorized by the investigators as mild, moderate, or severe will be categorized as Grade 1, Grade 2, or Grade 3, respectively. If a subject has a nonserious adverse event with unknown severity, then the subject will be counted in the severity grade level category of "unknown," even if the subject has another occurrence of the same event with a severity present. The only exception is if the subject has another occurrence of the same adverse event with the most extreme severity – "Severe." In this case, the subject will be counted under the "Grade 3" category. Similarly, if a subject has an adverse event with unknown seriousness, then the subject will be counted in the severity grade level category of "unknown" unless the subject has another occurrence of the same adverse event that is marked serious. In this case, the subject will be counted under the "Grade 4" category.

Adverse Event by Maximum Relationship

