Treatment-emergent adverse events also will be summarized by maximum relationship of each preferred term to study drug (DAA), as assessed by the investigator. If a subject has an adverse event with unknown relationship, then the subject will be counted in the relationship category of "unknown," even if the subject has another occurrence of the same event with a relationship present. The only exception is if the subject has another occurrence of the same adverse event with a relationship assessment of "Reasonable Possibility." In this case, the subject will be counted under the "Reasonable Possibility" category.

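### Three SAP adverse event summaries count drug-related events on DAA attribution alone, and no summary counts subjects with an event related to any study drug, ribavirin included

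*SAP*

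**What the plan says.** **Protocol.** Section 1.2 defines study drug as "Ombitasvir/ABT-450/r, sofosbuvir, ribavirin". Section 6.3 has the investigator judge causality twice: "Assessment of relatedness will be made with respect to the DAAs (ombitasvir/ABT-450/r and SOF) and with respect to RBV". Section 8.1.5.1 plans a tabulation by relationship to study drug, in which a subject with repeated events under one preferred term is counted once, using the "most related for the relationship to study drug table".

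**SAP 11.2.1.1.** Three summaries of drug-related events rest on the DAA assessment alone:

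- Adverse Event by PT: the only related-event version is for events related to DAAs. Of this group of tables the SAP says "These summaries will display for each treatment group and be sorted by overall total".
- Adverse Event by Maximum Severity: the related-event version covers events with a reasonable possibility of "being related to DAAs will be summarized by maximum severity of each preferred term".
- Adverse Event by Maximum Relationship: events are "summarized by maximum relationship of each preferred term to study drug (DAA), as assessed by the investigator".

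The same section also reports ribavirin attribution separately. The overview has a row, limited to ribavirin-containing arms, for events with a reasonable possibility "of being related to RBV", and there is a matching SOC/PT table by arm. In the overview and SOC/PT lists, the parenthesis after DAAs names only the ombitasvir/ABT-450/r tablet and leaves out sofosbuvir.

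**The concern.** The SAP's wording replaces study drug, which in this protocol includes ribavirin, with the DAAs. Taking DAAs as Protocol 6.3 defines them, a DAA-related event in Arm A or F is an event related to the regimen. In Arms B, C, D and E it is an event related to part of the regimen. The columns stand side by side, but the rule for counting an event as related covers different fractions of what the subjects took.

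This matters because Protocol 5.6.1 says the study will inform the role of ribavirin in the regimen, and Arm A versus Arm B is the only randomised contrast. The trial is open-label, so investigators know who takes ribavirin. The protocol also tells them that anemia in earlier trials was largely due to it (Section 3.0) and that hemoglobin reductions are a recognised ribavirin effect (Section 6.7.4). Ribavirin-only attribution is therefore foreseeable. Where it occurs, the event falls under no reasonable possibility in the relationship table and is absent from the related-event PT and severity tables.

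**Working it through.** The plan states no figure on this point, so there is none to reproduce. The check is a comparison of tables, followed by bounds.

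**1. Which attribution each summary uses (SAP 11.2.1.1)**

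| Summary | DAA-related | RBV-related | Any study drug |
|---|---|---|---|
| Overview | yes | yes (RBV arms) | no |
| SOC and PT | yes | yes | no |
| By PT | yes | no | no |
| By maximum severity | yes | no | no |
| By maximum relationship | yes | no | no |

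The last column is empty throughout. The last three rows are the summaries at issue.

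**2. Arms affected (SAP 4.2)**

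- With ribavirin: B, C and D at about 10 each and E at about 20, so 10 + 10 + 10 + 20 = 50.
- Without ribavirin: A and F at about 10 each, so 20.
- Total 50 + 20 = 70, which agrees with SAP 4.3.

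**3. How far a DAA-only count can fall short**

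Let D be the share of an arm with a DAA-related event, R the share with an RBV-related event, and U the share with an event related to either. Then

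max(D, R) ≤ U ≤ min(1, D + R),

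and the shortfall U − D lies between max(0, R − D) and min(R, 1 − D). In Arms A and F, R = 0 and the ribavirin shortfall is 0.

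The documents give no D or R for this regimen. The values below are assumptions, chosen to show the range:

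| D | R | U | Shortfall U − D |
|---|---|---|---|
| 0.6 | 0.1 | 0.60 to 0.70 | 0 to 0.10 |
| 0.4 | 0.3 | 0.40 to 0.70 | 0 to 0.30 |
| 0.2 | 0.5 | 0.50 to 0.70 | 0.30 to 0.50 |

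**4. Why the two separate tables do not settle it**

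Suppose 5 of 10 subjects have a DAA-related event and 5 have an RBV-related event. If they are the same five, the regimen-related count is 5. If they are different subjects, it is 10. Both cases give identical entries in the planned DAA and RBV tables. The ambiguity disappears only when one of the two counts is zero or the larger already equals the arm size.

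**5. Illustration only, from Protocol Table 2**

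The regimen-controlled columns give all-causality incidence with and without ribavirin. The excess share is (with − without) / with:

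- anemia (7.5 − 0.2)/7.5 = 97.3%
- insomnia (12.2 − 5.1)/12.2 = 58.2%
- asthenia (9.0 − 3.9)/9.0 = 56.7%
- pruritus (12.0 − 6.1)/12.0 = 49.2%
- nausea (15.7 − 8.4)/15.7 = 46.5%
- fatigue (29.9 − 26.5)/29.9 = 11.4%

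These figures come from genotype 1 subjects on a regimen containing dasabuvir, and they are not investigator attributions. They show that some event types rise with ribavirin. They do not estimate the shortfall here, which is zero if investigators mark both causes.

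**The case against.** The strongest reply is that ribavirin attribution is not lost. It has an overview row and a SOC/PT table by arm, which mirrors the two assessments collected under Protocol 6.3. The maximum-relationship table says openly that it is about the DAAs. Protocol 8.1.5.1 does not spell out a combined any-drug relationship, and Protocol 8.1 leaves detailed methods to the SAP. The analyses are descriptive, most arms have about 10 subjects, and no decision rule uses relatedness.

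Much of this stands, and it rules out two stronger readings.

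- A reader might infer that the SAP understates the harm of the ribavirin regimens overall. It does not. All treatment-emergent, serious, severe and Grade 3 or 4 events, events leading to discontinuation, and deaths are tabulated by arm whatever the attribution. So is anemia, as an event of special interest. Hemoglobin and bilirubin grades and RBV dose modifications are also summarised by arm. For Arm A versus Arm B in an open-label trial, these tables are the more reliable comparison.
- A reader might also infer that SAP 12.1 fails to declare a change from the protocol. That cannot be verified. Section 12.1 compares the SAP with the latest protocol version. The protocol supplied has two arms and about 20 subjects, whereas the SAP has six arms and about 70, so the SAP was written against a later protocol that is not available here.

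What the reply does not supply is a count of subjects with an event related to any study drug. Separate tables with overlapping subjects cannot give it. The supplied protocol's own definition still makes ribavirin part of the study drug to which its relationship table refers.

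**Conclusion.** The point holds for three summaries and one missing count. In Arms B to E, events attributed to ribavirin alone are not counted as related in the PT, maximum-severity and maximum-relationship summaries. Related-event rates there are not comparable with Arms A and F. The shortfall runs from zero to at most the RBV-related share of the arm, and its actual size cannot be determined from the documents.

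The statement that DAA attribution covers the whole regimen in Arms A and F assumes the Protocol 6.3 meaning, with sofosbuvir among the DAAs. On the SAP's literal parenthesis it would not, which is a second ambiguity to settle. It does not remove the ribavirin asymmetry.

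This is a cheap improvement to the reporting of drug-related events. It does not affect the all-causality safety results.

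**What to change.** In SAP 11.2.1.1:

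1. Derive a flag for related to any study drug, set when the investigator records a reasonable possibility for the DAAs or for ribavirin.
2. Add it as a row in the adverse event overview and as a SOC/PT table by arm.
3. Base the maximum-relationship table on it, in line with Protocol 8.1.5.1.
4. Show the related-event PT and maximum-severity tables on this flag alongside the DAA-only versions.
5. State that DAAs means ombitasvir/ABT-450/r and sofosbuvir, as in Protocol 6.3.

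Keep the separate DAA and RBV tables, which remain useful for attribution. Both causality fields are already collected, so the cost is SAP wording, one derived variable and a few more table rows. Drug-related percentages in the ribavirin arms may be higher than under the present wording, and the report should say that they count attribution to any component.

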11.2.2 Listing of Adverse Event

Listings of all serious adverse events (from the time the subject signed the study-specific informed consent through end of study), treatment-emergent serious adverse events,

treatment-emergent adverse events leading to death, treatment-emergent adverse events leading to discontinuation of study drug, treatment-emergent adverse events leading to RBV dose modifications, treatment-emergent adverse events leading to study drug interruptions, and treatment-emergent adverse events of special interest will be provided.

11.3 Analysis of Laboratory Data

Data collected from central and local laboratories, including additional lab testing due to all SAEs will be used in all analysis.

11.3.1 Variables and Criteria Defining Abnormality

Hematology variables include: hematocrit, hemoglobin, red blood cell (RBC) count, white blood cell (WBC) count, neutrophils, bands, lymphocytes, monocytes, basophils, eosinophils, platelet count, absolute neutrophil count (ANC), reticulocyte count, PT/INR, and activated partial thromboplastin time (aPTT).

Chemistry variables include: blood urea nitrogen (BUN), creatinine, total bilirubin, direct and indirect bilirubin, serum glutamic pyruvic transaminase (SGPT/ALT), serum glutamic oxaloacetic transaminase (SGOT/AST), alkaline phosphatase, sodium, potassium, calcium, inorganic phosphorus, uric acid, cholesterol, total protein, glucose, triglycerides, albumin, chloride, bicarbonate, magnesium, gamma glutamyl transferase (GGT), and creatinine clearance (Cockcroft-Gault calculation), calculation of estimated glomerular filtration rate (eGFR) using the modification of diet in renal disease (MDRD) equation as defined below, alpha2-macroglobulin, haptoglobin, and apolipoprotein A1.

Urinalysis variables include: specific gravity, ketones, pH, protein, blood, glucose, urobilinogen, bilirubin, leukocyte esterase, albumin, and microscopic (reflexly performed if other variables are abnormal).

Additional variables are total insulin and IP-10.

The following calculation is used by the central lab for eGFR by MDRD, where serum creatinine is measured in mg/dL and age is measured in years:

$$\text{GFR (mL/min/1.73 m}^2\text{)} = 175 \times \text{Serum Creatinine}^{-1.154} \times \text{Age}^{-0.203} \times 1.212 \text{ (if Black)} \\ \times 0.742 \text{ (if Female).}$$

The central lab calculates the estimated creatinine clearance (CrCl) based on the following Cockcroft-Gault formula:

$$\text{CrCl (mL/min)} = [(140 - \text{age}) \times (\text{weight in kg}) \times (0.85 \text{ if female})] / [\text{serum} \\ \text{creatinine (mg/dL)} \times 72].$$

The Criteria for Potentially Clinically Significant (PCS) Laboratory Findings are described in [Table 10](#) and [Table 11](#). Note that a post-baseline value must be more extreme than the baseline value to be considered a PCS finding.

Table 10. Criteria for Potentially Clinically Significant Hematology Values

Test/Units	Very Low (VL)	Very High (VH)
Hemoglobin		
(mmol/L)	< 4.9	
(g/dL)	< 8.0	
(g/L)	< 80	
Platelets Count		
(cells/mm ³)	< 50,000	
(cells/L)	< 50 × 10 ⁹	
White Blood Cell Count		
(cells/mm ³)	< 2000	> 20,000
(cells/L)	< 2.0 × 10 ⁹	> 20 × 10 ⁹
Absolute Neutrophil Count		
(cells/mm ³)	< 1000	
(cells/L)	< 1 × 10 ⁹	
Lymphocyte Count		
(cells/mm ³)	< 500	
(cells/L)	< 0.5 × 10 ⁹	
Eosinophil Count		
(cells/mm ³)		> 5000
(cells/L)		> 5 × 10 ⁹
aPTT		> 2 × ULN
International Normalized Ratio		> 2 × ULN

Note: A post-baseline value must be more extreme than the baseline value to be considered a PCS finding.

Table 11. Criteria for Potentially Clinically Significant Chemistry Values

Test/Units	Very Low (VL)	Very High (VH)
ALT/SGPT		$> 5 \times \text{ULN}$ and $\geq 2 \times \text{baseline}$
AST/SGOT		$> 5 \times \text{ULN}$ and $\geq 2 \times \text{baseline}$
Alkaline Phosphatase		$> 1.5 \times \text{ULN}$
Total Bilirubin (mg/dL)		$\geq 2.0 \times \text{ULN}$
Creatinine		
(mcmol/L)		≥ 132.605
(mg/dL)		≥ 1.5
Creatinine Clearance (mL/min)	< 50	
BUN		$> 5 \times \text{ULN}$
Uric Acid		
(mcmol/L)		> 713.817
(mg/dL)		> 12.0
Phosphate		
(mmol/L)	< 0.6	
(mg/dL)	< 2.0	
Calcium, Serum		
(mmol/L)	< 1.75	> 3.1
(mg/dL)	< 7.0	> 12.5
Sodium (mmol/L)	< 130	> 155
Potassium (mmol/L)	< 3.0	> 6.0
Magnesium		
(mmol/L)	< 0.4	> 1.23
(mg/dL)	< 0.9	> 3.0
Glucose		
(mmol/L)	< 2.2	> 13.9
(mg/dL)	< 40	> 250
Albumin		
(g/L)	< 20	
(g/dL)	< 2	

Table 11. Criteria for Potentially Clinically Significant Chemistry Values (Continued)

Test/Units	Very Low (VL)	Very High (VH)
Protein		
(g/L)	< 50	
(g/dL)	< 5.0	
Cholesterol		
(mmol/L)		> 10.34
(mg/dL)		> 400
Triglycerides		
(mmol/L)		> 5.7
(mg/dL)		> 500

Note: A post-baseline value must be more extreme than the baseline value to be considered a PCS finding.

